#### **4.5.4.2. Vital Signs**

Values of vital signs (temperature, systolic and diastolic blood pressure, pulse rate, respiratory rate, and oxygen saturation (measured by pulse oximetry) as well as the change from baseline will be summarized by scheduled visit using mean, median, standard deviation, minimum and maximum.

A summary of changes in heart rate comparing the baseline value to the worst-case post baseline value will be provided. Heart rate will be categorized into ‘Decrease to  $<60$ ’, ‘Change to Normal or No Change’ and ‘Increase to  $>100$ ’. The determination of the worst-case post baseline considers both scheduled and unscheduled assessments. If a

participant has a decrease to low and an increase to high, then the participant is counted in both the “Decrease to <60” categories and the “Increase to >100” categories.

In addition, summaries of grade increase in systolic blood pressure (SBP) and diastolic blood pressure (DBP) will be provided separately. These summaries will display the number and percentage of participants with any grade increase, increase to Grade 2 and increase to Grade 3 for worst-case post-baseline only. The grade definition for SBP (mmHg) is: Grade 0 (<120), Grade 1 (120-139), Grade 2 (140-159), Grade 3 ( $\geq$ 160). The grade definition for DBP is: Grade 0 (<80), Grade 1 (80-89), Grade 2 (90-99), Grade 3 ( $\geq$ 100). The summaries will be produced for worst-case post baseline only.

#### **4.5.4.3. ECG**

A listing of QTc values of potential clinical importance will be provided using the collected values based on Fridericia formula.

#### **4.5.4.4. Performance Status**

ECOG performance status will be summarized at baseline and each post-baseline scheduled visit. Summaries will use frequency and percentage of participants at each planned assessment time. A summary of change from baseline by scheduled visits will be performed, as well as the worst case post-baseline and the best case post-baseline changes during the study (improved, no change, deteriorated).

A supporting listing will also be provided.

#### **4.5.4.5. Pregnancies**

While pregnancy itself is not considered to be an AE or SAE, any pregnancy complication or elective termination of a pregnancy for medical reasons will be recorded as an AE or SAE as described in the protocol. If participants become pregnant while on the study, the information will be included in the narratives and no separate table or listing will be produced.

CCI

CCI

CCI

## 4.6. Other Analyses

### 4.6.1. Population Pharmacokinetic Analysis

Plasma belantamab mafodotin, total mAb, and/or cys-mcMMAF concentration-time data may be combined with data from other studies and analysed using a population pharmacokinetic approach. The initial analysis will use the population pharmacokinetic model developed for Study BMA117159 and Study 205678 to generate post hoc pharmacokinetic parameter estimates for the individual participants in Arm 1 of Study 207495. Based on the individual post hoc parameter values, dosing information, and sample collection times, belantamab mafodotin plasma concentrations at the time of sample collection will be predicted for each participant. Model evaluation will consist of comparison of model-predicted and observed concentrations. If necessary, model estimation or refinement will be performed.

Details of the population PK analyses will be reported under a separate RAP, and the results of this analysis will be provided in a separate report.

### 4.6.2. Subgroup analyses

#### 4.6.2.1. Subgroup analyses of PFS

Subgroup analyses of PFS will be based on the ITT analysis set.

The following subgroup analyses will be performed to compare the primary estimand of PFS between treatments, based on investigator-assessed response, respectively, if data permit.

Subgroup	Categories 
Previous treatment with anti-CD38 therapy 	Yes, No
ISS staging 	I/II; III
Number of prior lines of therapy 	≤3; >3
Previous treatment with anti-CD38 therapy and number of prior lines of therapy	Yes and >3; Other
Previous treatment with melphalan	Yes, No
Previous stem cell transplant	Yes, No
Age at randomization	<65, ≥65 to <75, ≥75 years age
Gender	Male, Female
Ethnicity	Hispanic, Non-Hispanic
Race	Black, White, Other
Region of Enrollment	North America, Europe, North East Asia, Rest of the world
Baseline renal impairment status per eGFR (ml/min/1.73 m  )	Normal (≥ 90), Mild (≥ 60, < 90), Moderate (≥ 30, < 60), Severe (≥ 15, < 30)
Type of myeloma	IgG, Non-IgG

Subgroup	Categories 
Baseline extramedullary disease	Yes, No
Cytogenetics Risk 	High, Other (non-high risk - all others)
Refractory to prior anti-cancer therapy	Any Proteasome Inhibitor (PI) Bortezomib Carfilzomib Ixazomib Any Immunomodulator (IMiD) Thalidomide Lenalidomide Pomalidomide Any Monoclonal Antibody Elotuzumab Isatuximab Daratumumab Daratumumab alone  Daratumumab in combination  PI+IMiD Anti-CD38 antibody+PI+IMiD

- [1]. If the percentage of participants is small within a particular subgroup, then the subgroup categories may be refined prior to unblinding the trial.
- [2]. Randomization factors
- [3]. A subject is considered as high risk if the subject has any of the following cytogenetics: t(4;14), t(14;16), and del(17p13).
- [4]. Defined as prior CTX regimen with Daratumumab as the only drug in the regimen.c
- [5]. Defined as prior CTX regimen with Daratumumab and other drugs.

Additional subgroups CCI may be assessed if there is clinical justification or an imbalance is observed between the treatment arms. The purpose of the subgroup analyses is to assess the consistency of treatment effect across expected prognostic factors.

The ITT analysis set will be used in the subgroup analyses. The subgroup analyses will be based on values recorded on the eCRF (or vendor data if collected outside of eCRF).

CCI

For each subgroup, the hazard ratio (HR) and 95% CI will be calculated from an unstratified Cox proportional hazards model with treatment as the only covariate. HR and 95% CI for each subgroup level will be provided separately; refer to Section 4.2.2 for the analysis method and the subgroup analysis will only be performed for PFS based on primary event/censoring rule. The HRs and associated two-sided 95% CIs will be summarized and presented on a forest plot, along with the results of the overall analysis (i.e. analysis based on the whole ITT analysis set).

If there are too few events available for a meaningful analysis of a particular subgroup (it is not considered appropriate to present analyses where there are less

than 20 events in a subgroup), the subgroup will not be formally analyzed by unstratified Cox proportional hazards model. In this case, only descriptive summaries will be provided.

Subgroup PFS analysis will be conducted at final PFS analysis.

**4.6.2.2. Subgroup analyses of OS**

Subgroup analyses of OS will be based on the ITT analysis set.

Subgroup OS analyses will be performed based on subgroups as specified in Section 4.6.2.1. The HRs and associated two-sided 95% CIs will be summarized and presented on a forest plot, along with the results of the overall analysis (i.e. analysis based on the whole ITT analysis set). Refer to Section 4.6.2.1. for subgroups and analysis details.

Subgroup OS analysis will be conducted at final OS analysis

**4.7. Planned Analyses**

Table 8 summarizes the planned analyses for PFS and OS.

**Table 8 Summary of PFS and OS analyses**

Analyses Timing from Randomization	Planned PFS analyses	Planned OS analyses
~25 months	PFS final ~151 PFS events	OS IA for efficacy ~100 OS events ~40% OS info
48 months	N/A	OS IA for efficacy b ~175 OS events ~70% OS info
>60 months	N/A	OS final b ~250 OS events

- a. Provided that final PFS analysis is significant.
- b. If PFS is significant and null hypothesis is not rejected at the 2nd OS IA for efficacy.
- c. First dose of 320th subject happens around 21 months

**Planned Analyses for Key secondary endpoint OS**

The key secondary efficacy endpoint, OS, will be compared between the 2 treatment arms (belantamab mafodotin arm vs pomalidomide/ dexamethasone arm) using a group sequential log-rank test corresponding to three analyses: one interim analysis at the same time of PFS final (~40% information), one interim analysis at ~70% information and one final at 100% information. The boundary for declaring superiority of belantamab mafodotin arm over pomalidomide/ dexamethasone arm is based on a Lan-DeMets (O’Brien-Fleming) alpha spending function [Lan, 1983] with overall alpha = 0.025, one-

tailed, and will be adjusted based on actual observed number of deaths (actual information fraction).

At the first OS interim analysis for efficacy (~40% OS information fraction), the study will not be stopped regardless of the results. The OS data will continue to be collected to conduct the 2nd OS interim analysis to test for efficacy at ~70% OS information fraction.

At the OS interim analysis for efficacy (~70% OS information fraction) (Table 9), assuming 175 events are observed, if the calculated  $p < 0.0073$  (corresponding to  $HR < 0.676$ ), it would be considered that the efficacy boundary is crossed and the OS analysis would be significant.

A hierarchical testing procedure will be adopted and the OS interim/final analysis for efficacy will only be performed if the primary efficacy endpoint PFS is statistically significant at PFS final analysis [Bretz, 2009; Li, 2017]. The testing procedures are detailed as follows:

Step 1: Test PFS at the final PFS analysis. If significant, go to Step 2 and overall one-sided alpha of 0.025 will be carried forward to test for OS; if not significant, stop testing;

Step 2: Test OS at the first OS interim analysis (at the same time of PFS final, ~40% OS information fraction) for efficacy. (cumulative one-sided alpha spent for OS = 0.0004)

Step 3: Test OS at the second OS interim analysis (~70% OS information fraction) for efficacy. If significant, stop testing; if not significant, go to Step 4. (cumulative one-sided alpha spent for OS = 0.0074)

Step 4: Test OS at the time of the final OS analysis (cumulative one-sided alpha spent for OS = 0.025).

**Table 9 Stopping boundaries for OS**

Information fraction	N of events	Cum. alpha Spent	Efficacy Boundary	Efficacy Boundary	Boundaries crossing probabilities (incremental)	
			(p-value)	(HR)	Under H0	Under H1
0.4	100	0.0004	0.0004*	0.491*	0.04%	5.8%
0.7	175	0.0074	0.0073	0.676	0.7%	41.2%
1	250	0.025	0.0227	0.765	1.8%	33.1%

\*: The threshold will be used for the 1st OS analysis, however, the study will not be stopped for efficacy regardless of the results. GSK will continue to collect the OS data to conduct the 2nd OS interim analysis to test for efficacy at ~70% OS information fraction.

If OS is significant at 70% IF, OS data will continue to be collected until end of study: defined as all participants have died, are lost to follow up, or withdrawn consent, or for 2 years after the OS analysis at ~70% IF, whichever occurs first. For the two scenarios above, analysis of OS will be performed at the end of study using only Kaplan-Meier method and stratified Cox proportional hazards model.

#### **4.7.1. Independent Data Monitoring Committee**

An Independent Data Monitoring Committee (IDMC) consisting of at least 2 physicians and one statistician as defined in the IDMC Charter will review data at defined time points. Additional details, including the list of outputs supporting decision making at the interim analysis, will be provided in the IDMC charter.

The first IDMC safety review meeting is planned when approximately 60 participants have been on study for at least 8 weeks. Subsequent IDMC safety review meeting is planned approximately every 6 months hereafter.

#### **4.8. Changes to Protocol Defined Analyses**

There were no changes or deviations to the originally planned statistical analysis specified in the protocol amendment 3 (Version: GSK Document Number [TMF-13954921](#), Dated: [20-SEP-2021]).

## 5. SAMPLE SIZE DETERMINATION

### 5.1. Statistical Hypotheses

#### Primary endpoint PFS

The primary efficacy analysis will be the comparison of the distribution of PFS between the two treatment groups. Assuming proportional hazards for PFS, the following statistical hypothesis will be tested to address the primary efficacy objective at one-sided alpha level of 2.5%:

$$H_{01}: \theta_1 \geq 1 \text{ VS. } H_{A1}: \theta_1 < 1$$

where,  $\theta_1$  is the PFS HR (belantamab mafodotin arm vs. pom/dex arm).

#### Key secondary endpoint OS

Assuming proportional hazards for OS, the following statistical hypotheses will be tested at one-sided alpha level of 2.5% if PFS is statistically significant:

$$H_{02}: \theta_2 \geq 1 \text{ VS. } H_{A2}: \theta_2 < 1$$

where,  $\theta_2$  is the OS HR (belantamab mafodotin arm vs. pom/dex arm).

### 5.2. Sample Size Determination

#### Primary Endpoint PFS

Based on available data from literature, the median PFS in the pom/dex arm is expected to be around 4 months [[San Miguel, 2013](#)]. It is expected that treatment with belantamab mafodotin will result in a 43% reduction in the hazard rate for PFS, i.e. an expected HR of 0.57 (corresponding to an increase in median PFS from 4 months to 7 months under the exponential model assumption).

The final PFS analysis will be conducted at the time of observing approximately 151 events and the first 320 randomized subjects have been followed for a minimum of 4 months. With 151 events, the study has a power of 90% to detect a hazard ratio of 0.57 at 1-sided alpha of 0.025 (corresponding to a critical value of 0.713 for the hazard ratio). This calculation assumes participants randomized to the two treatment arms in a 2:1 ratio. Assuming that enrolment will continue for approximately 20 months at a uniform rate of 16 participants per month, a total of 320 participants will be randomized in a 2:1 ratio to receive single agent belantamab mafodotin or pom/dex. It is estimated that the targeted 151 PFS events will be observed approximately 23 months after the first participant is randomized based on a lognormal cure rate model ([Chen, 2016](#)). These calculations were made using the software package East 6.5 and a proprietary SAS macro.

## Power for Analysis of Key Secondary Endpoint OS

OS, as the key secondary endpoint, will be formally statistically tested, provided that the primary endpoint PFS is statistically significant. Based on available data from literature, the median OS in the pom/dex arm is expected to be around 13 months [San Miguel, 2013]. It is hypothesized that treatment with belantamab mafodotin will result in a 32% reduction in the hazard rate for OS, i.e., an expected HR of 0.68 (which corresponds to an increase in median OS to 19 months under the exponential model assumption). In order to ensure 80% power to test the null hypothesis: OS HR = 1, versus the specific alternative hypothesis: OS HR = 0.68, a total of 250 deaths need to be observed. This calculation assumes analysis by a one-sided log-rank test at the overall 2.5% level of significance, participants randomized to the two treatment arms in a 2:1 allocation ratio, and a group sequential design with a Lan-DeMets (O'Brien-Fleming) alpha spending function [Lan, 1983] using information fractions of (0.4, 0.7, 1). Based on the same number of participants that are planned to be enrolled in this study to provide sufficient power for the primary endpoint (i.e., 320 participants), it is estimated that these 250 deaths will be observed approximately 55 months after the randomization date of the first participant under  $H_{A2}$  (assuming a similar loss to follow-up, i.e. 5% per year). Therefore, the cut-off date for the final analysis of OS will be approximately 35 months after the cut-off date for the final analysis of PFS. These calculations were made using the software package East 6.5.

If the number of participants required by local regulatory agencies are not recruited within the planned recruitment target, enrolment may continue in separate cohorts until the country enrolment requirements, as required by local regulatory bodies, have been reached. Additional participants that are enrolled in separate cohorts will not be included in the analysis portion of the study planned for the marketing application, which is based on approximately 151 events. However, these additional participants will be included in country-specific supplemental analyses, as detailed in country specific Statistical Analysis Plan (SAP), requested by the applicable regulatory authorities concerned.

## **6. SUPPORTING DOCUMENTATION**

### **6.1. Appendix 1 Study Population Analyses**

Unless otherwise specified, the study population analyses will be based on the ITT Analysis Set. Study population analyses including analyses of subject's disposition, protocol deviations, demographic and baseline characteristics, prior and concomitant medications, and subsequent anti-cancer therapy will be based on GSK Core Data Standards.

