### 3. ANALYSIS SETS

Analysis Set	Definition / Criteria	Analyses Evaluated
All Screened	
 
The All Screened Population will consist of all participants who sign the ICF to participate in the clinical trial. Participants in this population will be used for screen failure summary.
 
	
 
Study Population
 

Enrolled	
 
All participants who entered the study.
 
Note screening failures (who never passed screening even if rescreened) and participants screened but never enrolled into the study (Reserve, Not Used) are excluded from the Enrolled analysis set as they did not enter the study.
 
	
 
Study Population
 

Intent-to-Treat (ITT)	
 
ITT Population will consist of all randomized participants whether or not randomized treatment was administered. This population will be based on the treatment and strata to which the participant was randomized and will be the primary population for the analysis of efficacy data. Any participant who receives a treatment randomization number will be considered to have been randomized.
 
	
 
Study Population
 
Efficacy
 

mITT (modified ITT)	
 
All participants who have received at least 2 lines of prior therapies; randomized and received at least one dose of study treatment (participant randomized to the belantamab mafodotin arm but received pom/dex will be excluded and vice versa); with measurable disease at baseline.
 
	
 
Efficacy
 

Safety	
 
All randomized participants who take at least 1 dose of study intervention (any drug component). Participants will be analyzed according to the intervention they actually received.
 
	
 
Safety
 

Pharmacokinetic (PK)	
 
All participants in the Safety analysis set who had at least 1 non-missing PK assessment (Non-quantifiable [NQ] values will be considered as non-missing values).
 
Data should be reported according to the actual treatment
 
	
 
PK
 

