## **4. STATISTICAL ANALYSES**

### **4.1. General Considerations**

#### **4.1.1. General Methodology**

The Intent-to-Treat (ITT) analysis set will be used for all study population analyses and efficacy analyses, unless otherwise specified and Safety analysis set will be used for all safety analyses.

The stratified log-rank test and stratified Cox proportional hazards models will include the randomization stratification factors as “strata”. Unless otherwise specified, the stratification factors entered for randomization will be used in the primary analysis. If there is any mis-stratification, a supplementary analysis will be performed using the stratification data based on the clinical database.

Confidence intervals will use 95% confidence levels unless otherwise specified.

Unless otherwise specified, continuous data will be summarized using descriptive statistics: n, mean, standard deviation (std), median, minimum and maximum. Categorical data will be summarized as the number and percentage of participants in each category.

For efficacy analyses, only central lab values will be used.

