## **4.5. Safety Analyses**

The safety analyses will be based on the Safety Analysis Set, unless otherwise specified.

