### **6.1.4. Prior and Concomitant Medications**

Concomitant medications will be coded using both the GSK Drug and WHO Drug dictionaries. However, the summary will be based on GSK Drug dictionary only. The summary of concomitant medications will show the number and percentage of participants taking concomitant medications by Ingredient. Multi-ingredient products will

be summarized by their separate ingredients rather than as a combination of ingredients. Anatomical Therapeutic Chemical (ATC) classification Level 1 (Body System) information will be included in the dataset created but will not appear on the listing or summary.

In the summary of concomitant medications, each subject is counted once within each unique ingredient. For example, if a subject takes Amoxicillin on two separate occasions, the subject is counted only once under the ingredient “Amoxicillin”. In the summary of concomitant medications, the ingredients will be summarized by the base only, using CMBASECD and CMBASE. Note: In order to be considered a concomitant medication, the concomitant medication must have been taken at some point during the on-treatment window.

Prophylactic medication for infusion-related reactions and prophylactic topical eye medications will be summarized by drug class and drug name and listed separately.

Blood products or blood supportive care products with onset date within the on-treatment window will be included in the summary tables. The frequency and percentage of participants using blood products and blood supportive care products after the start of study medication will be provided. Supporting listings will also be provided.

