### 6.2.2. Study Period

Assessments and events will be classified according to the date/time of occurrence relative to date/time of first dose of study treatment.

Study Phase	Definition
Pre-Treatment	Date/time $\leq$ Study Treatment Start Date/time
On-Treatment	Study Treatment Start Date/time < Date/time $\leq$ Last Dose Date + 70 days
Post-Treatment	Date/time > Study Treatment Stop Date + 70 days

For assessment or event on the first dosing day, whether it is Pre-Treatment or On-Treatment should be based on time if available. If time is not available, the first dosing day (Day 1) is considered Pre-Treatment for ECOG, ECG, vital signs, liver events, lab tests, cardiac scan, and other safety domains, and On-Treatment for adverse events and concomitant medications.

Concomitant Medication and Blood and Blood Supportive Care Product start and end dates will be assigned to study time periods in relation to first dose of study treatment as defined below. The start date references time flag variables and end date reference time flag variables will be added to the concomitant medications and blood and blood supportive products datasets, respectively.

- Start relative to treatment: Assign to 'BEFORE' if start date is prior to study treatment start date or if subject has not taken any study treatment or (start date is missing and end date is before study treatment start date). Else assign to 'DURING' if the start date falls into the on-treatment period as defined above or if subject is ongoing (not all study treatment discontinuation records completed) or start date is missing. Else assign to 'AFTER' if start date is after the on-treatment period.
- End relative to treatment: Assign to 'BEFORE' if end date is prior to study treatment start date or if subject has not taken any study treatment. Else assign to 'DURING' if start date falls into the on-treatment period or if subject is ongoing (not all study treatment discontinuation records completed) or (end date is missing and start relative to treatment not 'AFTER'). Else assign to 'AFTER' if start date is after the on-treatment period or (end date is missing and start relative to treatment='AFTER').

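### Concomitant-medication and blood-product percentages are set on the ITT population, although the SAP's own flags keep undosed participants out of every numerator

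*SAP*

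**What the plan says.** **Denominator.** SAP section 4.1.1 sets the general rule: "The Intent-to-Treat (ITT) analysis set will be used for all study population analyses and efficacy analyses, unless otherwise specified". Section 6.1 repeats it ("Unless otherwise specified, the study population analyses will be based on the ITT Analysis Set") and names the topics covered, ending with "prior and concomitant medications, and subsequent anti-cancer therapy will be based on GSK Core Data Standards". Section 6.1.4 covers concomitant medications, prophylactic medication, blood products and blood supportive care, and names no other set. Section 3 defines the default: "ITT Population will consist of all randomized participants whether or not randomized treatment was administered". ITT participants are grouped by the arm to which they were randomised.

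**Numerator.** Section 6.1.4 counts a drug as concomitant only if it was taken at some time in the on-treatment window. For blood products it says: "The frequency and percentage of participants using blood products and blood supportive care products after the start of study medication will be provided". Section 6.2.2 puts this into effect with a start flag and an end flag. Both are set to BEFORE "if subject has not taken any study treatment".

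**Safety tables.** Section 4.5 says: "The safety analyses will be based on the Safety Analysis Set, unless otherwise specified". Section 3 defines that set as "All randomized participants who take at least 1 dose of study intervention (any drug component"), analysed by the treatment actually received.

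**The concern.** These summaries describe use during treatment, yet the stated denominator includes people who had no treatment period. Under the SAP's own flags such a person cannot be counted as a user, whatever medication or transfusion was recorded. The result is a diluted percentage produced by a stated rule. It is not a gap in detail.

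The practical cost is comparability. A reader of the report may well set transfusion and supportive-drug use beside the thrombocytopenia and other adverse-event tables. Those use treated participants, grouped by what they received, while the medication tables use all randomised participants, grouped by assignment. Nothing in the SAP warns the reader of the change of base.

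**Working it through.** **1. Inputs.** Section 1.2 plans about 320 participants randomised 2:1, with about 214 on belantamab mafodotin and 106 on pom/dex. Check: 320 × 2/3 = 213.3 and 320 × 1/3 = 106.7, which agrees with the stated sizes to rounding. The SAP gives no number or proportion never dosed and no expected rate of medication use, so both are assumed below.

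**2. Can an undosed participant be counted?** Setting the flags in section 6.2.2 beside its selection rules:

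| Summary | Flags of an undosed participant (start / end) | Flags required | Counted? |
|---|---|---|---|
| Concomitant medications | BEFORE / BEFORE | start BEFORE or DURING; end DURING or AFTER | No, fails on end |
| Concomitant medications with on-therapy onset | BEFORE / BEFORE | start DURING; end DURING or AFTER | No, fails on both |
| Blood and blood supportive care products | BEFORE / BEFORE | start DURING; end DURING or AFTER | No, fails on both |

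The BEFORE condition is the first branch of each rule, so no later branch can override it. Applying the rules for the main concomitant-medication summary and the blood-product summary to a grid of start and end dates, missing dates included, gave 0 records of an undosed participant passing either filter.

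**3. Size of the shortfall.** Let n be the number randomised to an arm, u the number never dosed, and p the proportion of treated participants who use the product. For this calculation, treated participants are taken to have received their assigned regimen.

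- Reported proportion = p × (n − u)/n
- Relative understatement = u/n
- Shortfall in percentage points = 100 × p × u/n

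For an assumed untreated fraction u/n of 1% to 5%:

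| True use among treated | Reported at 1% untreated | Reported at 5% untreated |
|---|---|---|
| 20% | 19.8% | 19.0% |
| 40% | 39.6% | 38.0% |
| 50% | 49.5% | 47.5% |
| 90% | 89.1% | 85.5% |

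The largest shortfall in this range is 0.90 × 5% = 4.5 percentage points.

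**4. Do the arms differ?** The relative understatement is u/n in each arm, so equal untreated fractions give equal relative understatement whatever the arm sizes.

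- 3 undosed in each arm: 3/214 = 1.4% and 3/106 = 2.8%, larger in pom/dex.
- 6 undosed on belantamab mafodotin and 2 on pom/dex: 6/214 = 2.8% and 2/106 = 1.9%, larger on belantamab mafodotin.
- Break-even: 214/106 = 2.02. Pom/dex is affected more only if the belantamab mafodotin arm has fewer than about 2.02 times as many undosed participants.

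**5. After the change.** With a treated denominator, (n − u)/n is replaced by 1 and the understatement is zero in both arms.

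**The case against.** The best defence is that this is a disclosed convention. A percentage of all randomised participants is correct if labelled ITT; it is low only for a reader who wants use among the treated. Section 6.1.1 requires the number in each analysis set to be reported, so the gap between ITT and Safety will be visible. Section 6.1 also refers to the sponsor's core data standards and section 1 leaves display details to the Output and Programming Specification. Neither document is to hand, and either might name another set.

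Part of this stands: the figure can be interpreted, and a careful reader could rescale it. But the ITT sentence is explicit and 6.1.4 makes no exception, although the SAP does name another set where it wants one (for example, Safety for immunogenicity in 4.3.4). If the unseen standards use a treated denominator, the SAP text conflicts with them and still needs correcting. Disclosure also does not explain why the numerator is limited to treated people and the denominator is not.

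Three stronger readings are tempting, and the document does not support them:

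- **That pom/dex is understated more because it is the smaller arm.** Arm size alone produces no difference (step 4). Entering the same undosed count in both arms assumes a rate about twice as high in pom/dex. The SAP gives no figure or expectation for either arm.
- **That the flags also exclude users from the prophylaxis tables.** For infusion-reaction and eye prophylaxis, 6.1.4 states no window, and the selection rules in 6.2.2 do not name those tables. The argument there is consistency only.
- **That use will be materially credited to the wrong drug.** ITT grouping would do this for anyone given the other regimen, but the SAP gives no indication that this will happen or how often.

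**Conclusion.** The point holds for the concomitant-medication, blood-product and blood supportive care summaries. As written, each percentage understates use among treated participants by the untreated fraction of that arm, and its denominator and arm grouping differ from those of the adverse-event tables. If nobody goes undosed the understatement is zero. With 1-5% undosed, which is an assumption, a true 40% is reported as 39.6-38.0%. Any difference between arms depends on their untreated fractions and has no known direction. The matter is minor: the tables are descriptive, and no hypothesis test, estimand, efficacy result or adverse-event table is affected. It merits a correction because the remedy is almost free.

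**What to change.** In SAP section 6.1.4, add a sentence stating that the on-treatment concomitant-medication, blood-product and blood supportive care summaries use the Safety Analysis Set, grouped by treatment received. For consistency, the summaries of infusion-reaction and eye prophylaxis can use the same set, since they relate to dosing. Keep ITT for baseline characteristics, prior therapy, disposition and subsequent anti-cancer therapy. The cost is one sentence in the SAP and a change of population setting in the affected table programs. Nothing is lost in the efficacy or remaining study-population outputs.
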